## *Background*

The United States Department of Health and Human Services has declared a national opioid crisis as over 130 Americans die every day from an opioid overdose. Opioid use disorder usually starts with a prescription for opioids for a valid medical condition. Severe or refractory pain, as well as longer durations and higher doses of initial opioid therapies increase the risk for opioid use disorder. Patients with acute TBI may be at particular high risk for opioid use disorder. Headache is the most common complaint after TBI, present in up to 90% patients. The pain is typically severe, persistent, and refractory to medical therapies. While opioids are not recommended in headaches associated with mild TBI, data suggest that they are commonly prescribed. The long-term consequences of unabated pain and high opioid exposure in TBI patients are uncertain. Among soldiers returning from active duty who have a TBI diagnosis, nearly 60% are prescribed an opioid during the post-deployment year. We believe it is pivotal to develop novel, non-pharmacological therapeutics that effectively manage pain and reduce opioid use in the acute phase in order to mitigate risk for chronic opioid use disorder. VR has shown promise as a non-pharmacologic pain modifier. In a prior collaboration with the [name] lab from the University of Maryland School of Nursing, we have shown that a VR environment can increase pain tolerance.

Physicians have utilized VR as a powerful distraction tool during painful procedures such as wound cleaning in burn patients, cystoscopy in urological patients, and physical therapy in orthopedic trauma patients. Hospitalized patients with persistent pain from orthopedic traumatic injuries, burns, and other complaints have benefitted from the addition of VR outside

of procedural distraction. Outpatients with chronic pain syndromes including chronic headache may also benefit. No one has previously studied the effect of VR on TBI induced headache pain.

### *Aims*

Aim 1a) Assess the feasibility and explore the effects of immersive virtual reality (VR) on pain after acute traumatic injury including TBI. We will test this aim by comparing the change in numeric pain rating scale pre- and post-immersive virtual reality scenarios to the change in numeric pain rating scales pre- and post- non-immersive two-dimensional tablet-based mimics and content-less virtual reality sensory immersion.

Aim 1b) Compare effectiveness of VR therapy to non-immersive control sessions in reducing opioid use.

Aim 1c) Compare VR therapy to non-immersive control sessions on pain-related affective measures (depression and anxiety), autonomic measures (heart rate variability, pupillometry), and subjective experience measures (perceived effectiveness, anxiety). These processes have been associated with pain experience but have not been adequately explored in past virtual reality studies.

### *Eligibility Criteria*

#### Inclusion Criteria

Diagnosis of Traumatic Injury (including but not limited to traumatic brain injury)

Age greater than or equal to 18 years-old

Endorsing at least moderate pain as defined by documentation of at least one numeric rating pain scale score of 3 or more in the last 24 hours.

Glasgow Coma Scale of 15

Expected to stay in the hospital for at least twelve hours after enrollment

### Exclusion Criteria

Seizure prior to enrollment

Pregnancy

non-English speaking

known intolerance of Virtual Reality

Participants should be able to consent for themselves

### *Procedures*

Patients who are enrolled in the study will be identified as candidates via the PI or Sub-Investigator, or Research Coordinator. Once the patient has been identified, the research coordinator, PI, or Sub-Investigator will approach the patient and discuss the research protocol with them. If the patient agrees to participate, the study coordinator will make sure that all of the appropriate documentation (including consent) is completed before study procedures begin.

After the consent has been signed and completed, the study participant will complete a pre-study questionnaire to elicit their prior experience with the proposed therapeutic as well as several validated scales of pain, nausea, anxiety and depression, gaming addiction, suggestibility, and expectancy. They will then be given a tutorial on how to use the Virtual Reality Headset, or Head Mounted Display (HMD). The HMD that will be used for this study protocol is not limited to just the Oculus Rift or Rift S, but may also be the Samsung Odyssey Plus, and HTC Vive Pro. The research staff will go over specifics on how to use the HMD, and will remain throughout the duration of time the participant is in the virtual reality world in case they have any questions or concerns.

Once the participant is acquainted with the HMD, by completing their guided tutorial on how to use the headset, he or she will take part in two virtual reality sessions and two non-immersive tablet-based control sessions. One session will be meditative, where the second session will be chosen during the participants tutorial/introduction to the HMD. This environment could be a game, music, or relaxing. There will be two sessions per day including one virtual reality session and one non-immersive tablet based sessions. The virtual reality sessions and non-immersive tablet-based sessions will take place within the duration of their hospitalization. Sessions will be randomized using internet-based randomization techniques, or through mathematical programs. Participants will be allowed to complete more sessions if they desire once they complete their initial 2 VR sessions and 2 tablet-based sessions.

[figure not shown]
To be completely immersed during the sessions, the patient will also be given the option to use Noise Cancelling Headphones during the study. Some HMD headsets come with headphones attached, and some do not. The Noise Cancelling Headphones will be used with the HMD's

without headphones attached, as well as with the tablet. This will block out hospital noises, and all other forms of communication so that they can be completely immersed in their environment. If the patient needs to communicate with the Research Coordinator or any clinical team member who is at the bedside, they will be instructed to remove the Noise Cancelling headphones so that they can voice their questions or concerns.

Before and after each session, participants will answer simple questions via questionnaire (included later in this application). The patient's heart rate, blood pressure, respiratory rate, and pupil size and reactivity will be recorded before and after each session to monitor response. Opioid usage and continuous heart rate will also be collected after each VR session. This is not just limited to the scheduled VR sessions - opioid usage and continuous HR can be taken at other non-scheduled VR sessions. This will vary on a patient-to-patient basis - being that some patients may want to participate more with VR after their 2 VR:2 tablet scheduled sessions, and some may not. Pain will be assessed every 2 hours by nurses using the Numeric Rating Scale with additional assessment directly before and after each study session.

All patients will have orders for analgesia written by the treatment team. If pain is inadequately controlled, additional analgesic orders will be placed by the clinical team in communication with the research team. Should pain ratings be increased after study sessions, the nurses will notify both the clinical and research teams for assessment.

At the conclusion of all sessions, participants will complete another questionnaire to help us understand their self-perceived experience of using virtual reality.

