5. Although uncommon, patients could potentially experience seizure like activity while using the HMD. Of note, the HMDs are widely available and used by the public in everyday life and require no special screening or monitoring for seizure in their use. Per the Oculus Rift product description, "Some people (about 1 in 4000) may have severe dizziness, seizures, eye or muscle twitching or blackouts triggered by light flashes or patterns, and this may occur while they are watching TV, playing video games or experiencing virtual reality, even if they have never had a seizure or blackout before or have no history of seizures or epilepsy". The PI and research personnel will ensure that patients do not suffer from seizures prior to their enrollment. During the study protocol procedures, the patient will be monitored in a hospital bed where there is extensive experience in monitoring for and treating seizures. Seizures from virtual reality headset use are known to occur in patients with photosensitive epilepsies. Traumatic brain injury is not known to produce photosensitive epilepsy. If at any time, the patient develops severe dizziness, seizures, eye or muscle twitching or blackouts triggered by light flashes or patterns the virtual reality headset will be removed and the study will be discontinued in the patient.

*Primary and Secondary Analyses*

Descriptive statistics will be used to describe the patient population. The primary outcome (Aim 1a) is the difference in change in pre- and post-session pain scores in the immersive virtual reality sessions as compared to control sessions. Secondary outcomes will include opioid usage (Aim 1b), affective measures (mood and anxiety), autonomic measures, and subjective experience measures (Aim 1c). We will use mixed effect models to analyze the differences between the ratings over time. This model allows us to run analyses utilizing all subjects despite some missing measurements (which can be expected when studying patients in an ICU setting). To investigate if demographics or patient measures of gaming addiction, suggestibility, or expectancy are related to the pain effect, we will use Pearson's correlation between the questionnaire scores and the difference of the means of both conditions and virtual reality sessions.

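### Heart rate variability is named as an Aim 1c outcome, but the stated measurements do not support comparing it between VR and tablet sessions

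*Combined protocol and SAP*

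**What the plan says.** The Aims section gives the contrast for Aim 1c, "Compare VR therapy to non-immersive control sessions on pain-related affective measures (depression and anxiety", and goes on to list "autonomic measures (heart rate variability, pupillometry" among the outcomes. Heart rate variability and pupillometry are therefore the two named autonomic outcomes, and both are to be compared between conditions.

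The Procedures section schedules two VR and two tablet sessions per participant. On measurement it makes three statements:

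- For all sessions: "The patient's heart rate, blood pressure, respiratory rate, and pupil size and reactivity will be recorded before and after each session to monitor response".
- For VR sessions: "Opioid usage and continuous heart rate will also be collected after each VR session".
- For optional extra sessions: "opioid usage and continuous HR can be taken at other non-scheduled VR sessions".

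Primary and Secondary Analyses carries the outcome forward as "autonomic measures, and subjective experience measures (Aim 1c". It gives no variability metric, recording length or window. The only outcome defined there as a before-to-after change is pain: "difference in change in pre- and post-session pain scores in the immersive virtual reality sessions as compared to control sessions".

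**The concern.** Heart rate variability is the variation in the interval between successive beats (the RR interval). To compare it between conditions, a trial needs beat-to-beat data, or something close to them, from comparable periods in both conditions. The plan names the outcome, but its measurement text does not provide those data. It provides a heart rate in both conditions and a continuous heart rate in one.

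This is more than missing detail. An undefined summary statistic can be chosen later, before the data are seen. A signal that was not saved at the bedside cannot be recovered. A team following the text could finish enrolment with a change in heart rate for every session and nothing from which to compute variability under control. Aim 1c could then be answered for pupillometry but not for heart rate variability. There would also be a temptation to report whatever can be extracted from the VR sessions alone, which is not a comparison.

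**Working it through.** The plan gives no figure to reproduce here, so the check sets the named outcome against the stated measurements.

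**Step 1. What the outcome needs.** Aim 1c asks for VR against control. The minimum is a variability measure from both conditions. A baseline-adjusted comparison also needs one before each session in both conditions.

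**Step 2. What is stated, by window.** Two VR and two tablet sessions make 2 + 2 = 4 scheduled sessions. With one window before and one after each, there are 4 × 2 = 8 windows per participant.

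| Window | Number | Heart rate with vital signs | Pupil measures | Continuous heart rate |
|---|---|---|---|---|
| Before VR | 2 | yes | yes | not stated |
| After VR | 2 | yes | yes | yes |
| Before tablet | 2 | yes | yes | not stated |
| After tablet | 2 | yes | yes | not stated |

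Heart rate and pupil measures are stated for 8 of 8 windows. Continuous heart rate is stated for 2 of 8, both in the VR condition, and for 0 of the 4 tablet windows. The statement about extra sessions concerns VR only and adds no control data.

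**Step 3. Whether the heart rate in all 8 windows can stand in.** It cannot. As an illustration, a rate of 75 bpm is a mean RR interval of 60000/75 = 800 ms. A series constant at 800 ms and a series alternating between 750 and 850 ms both have mean 800 ms and rate 75 bpm. Their successive differences are 0 ms and 100 ms, so the root mean square of successive differences (RMSSD) is 0 ms in one and 100 ms in the other. The same rate is compatible with very different variability. A rate before and a rate after give a change in rate and nothing else.

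**Step 4. Whether the continuous measure can stand in.** It might, if it is stored beat to beat or at fine time resolution. The available text does not mention ECG, RR intervals, a device for this signal, or a storage interval.

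**Step 5. The two readings of the continuous measure.**

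- If it is a recording made after the session, there is a post-session series for VR, no baseline, and nothing for tablet.
- If it is retrieval, after the session, of a trace that also covers earlier time, VR may have both windows (4 of 8). Tablet still has 0 of 4.

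Under neither reading does the stated schedule supply the control side.

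**Step 6. The other autonomic outcome.** Pupil measures are stated before and after each session in both conditions, so pupillometry can be compared as Aim 1c intends.

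**The case against.** The strongest reply is that the wording is loose rather than the data absent. The sentence on continuous heart rate shares its verb with opioid usage, which is naturally a record pulled afterwards. The following sentence speaks of taking continuous heart rate at sessions. Hospital monitoring could well yield a trace that spans the time before, during and after a session. This stands as far as it goes: the missing VR baseline may be only apparent. It does not supply tablet data. The wording on VR sessions could be shorthand for all study sessions, but the sentence just before it refers to each session without restriction, and the same paragraph names tablet sessions when it means them.

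Three stronger conclusions are tempting, and the documents do not support them.

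- A reader might infer that a before-to-after change in variability is a planned endpoint that is impossible to form. The plan never defines variability as such a change; only pain is defined that way. Since later retrieval of a longer trace is a possible reading, the text supports *not supported by the stated measurements*, not *impossible*.
- A reader might infer that the autonomic part of Aim 1c fails as a whole. It does not, because pupillometry is measured in both conditions.
- A reader might infer that any variability computed from a stored heart rate trend would be worthless, and put a number on the loss. That depends on the averaging interval, which the documents do not give. Fine resolution would keep much of the variation and coarse averaging would remove most of it, so no figure is offered.

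It is also fair to say that this is one component of one secondary outcome in a study framed as feasibility and exploration. That limits the weight of the point but does not remove it.

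**Conclusion.** The point holds in a limited form. Heart rate variability is a named outcome for a VR-versus-control comparison, and the stated measurements do not support that comparison, with or without baseline adjustment. Continuous heart rate is stated for 2 of 8 scheduled windows per participant (at most 4 of 8 on the retrieval reading), for none of the 4 tablet windows, and without a statement that beat-to-beat data are kept.

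This rests on the readable text of the Aims, Procedures, and Primary and Secondary Analyses sections. A figure in the Procedures section is not shown in the copy reviewed, so it could not be checked whether it adds recordings. If tablet sessions are in fact recorded in the same way and RR data are saved, the remedy is only to say so and to define the summary.

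The primary pain outcome, the heart rate comparison and pupillometry are not affected. The sponsor should make the change, because uncaptured data are lost for good, but it does not threaten the main conclusion of the trial.

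**What to change.** Take one of two routes.

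**Keep the outcome.** In Procedures, state that beat-to-beat (RR) data will be saved for the same fixed resting window before and after every scheduled session, VR and tablet alike. In Primary and Secondary Analyses, name one variability summary, for example log RMSSD, to be compared between conditions in the planned mixed model with the pre-session value as baseline. The choice of summary and window length is the sponsor's; what matters is that both are fixed in advance and identical across conditions. The cost is a few extra resting minutes per session and confirmation that the monitors can export RR intervals.

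**Drop the outcome.** If the monitors cannot export beat-to-beat data, replace heart rate variability with heart rate in Aim 1c and make no variability claim. Procedures already records heart rate before and after each session in both conditions, so this needs no new data. The cost is the loss of the variability claim.

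On either route, reword the sentence on continuous heart rate to say when it is recorded, as distinct from when it is retrieved, and whether tablet sessions are included.

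### Procedures plans opioid use and continuous heart rate after VR sessions and does not mention tablet sessions, although Aim 1b and, by inference, part of Aim 1c compare the two

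*Combined protocol and SAP*

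**What the plan says.** All places are in the combined protocol and SAP.

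- **Aims.** Aim 1b is to "Compare effectiveness of VR therapy to non-immersive control sessions in reducing opioid use". Aim 1c makes the same comparison for several groups of measures, among them "autonomic measures (heart rate variability, pupillometry").
- **Procedures, schedule.** Each participant has two VR and two tablet-based control sessions: "There will be two sessions per day including one virtual reality session and one non-immersive tablet based sessions". On allocation: "Sessions will be randomized using internet-based randomization techniques, or through mathematical programs". Participants who want more sessions may have them after these four.
- **Procedures, measurements.** Vital signs and pupil measures "will be recorded before and after each session to monitor response". Pain is scored by nurses every 2 hours, "with additional assessment directly before and after each study session". For the other two measures the text is "Opioid usage and continuous heart rate will also be collected after each VR session", followed by the statement that "opioid usage and continuous HR can be taken at other non-scheduled VR sessions".
- **Primary and Secondary Analyses.** Opioid usage and autonomic measures are secondary outcomes, analysed with mixed effect models that are said to accommodate some missing measurements. No collection schedule is given there.

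**The concern.** A comparison of VR with control sessions needs the outcome measured under both conditions. For opioid use and continuous heart rate, the collection rule names VR sessions, and the sentence that widens it names VR sessions again. The same paragraph uses general terms that cover every session for the other measures, and it distinguishes VR from tablet sessions when it counts the scheduled ones. Staff who follow it could therefore reasonably collect these two measures after VR sessions and not after tablet sessions.

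At stake are two secondary contrasts: opioid use (Aim 1b) and heart rate variability (part of Aim 1c). A related gap affects opioid use even if tablet sessions are added. The two conditions fall on the same day, and the text gives no window that would tie a dose to one session or the other.

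**Working it through.** The plan gives no figure to reproduce here. The check is a side-by-side reading, followed by simple counting.

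**Step 1. Coverage by measure.** Scheduled sessions per completer: 2 VR + 2 tablet = 4 (Procedures).

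| Measure | Sessions named in Procedures | VR | Tablet | Used in |
|---|---|---|---|---|
| Pain score | every study session | 2 | 2 | Aim 1a (primary) |
| Heart rate, blood pressure, respiratory rate | every session | 2 | 2 | monitoring of response |
| Pupil size and reactivity | every session | 2 | 2 | Aim 1c |
| Opioid use | VR sessions | 2 | none named | Aim 1b |
| Continuous heart rate | VR sessions | 2 | none named | Aim 1c, if it is the source of heart rate variability |

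Read literally, the last two measures are planned at 2 of the 4 scheduled sessions, and the others at 4 of 4. No other readable section plans either measure for tablet sessions.

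**Step 2. Consequence for the model, if there are no tablet data.** Write the fixed part as a + b × VR, where VR is 1 for a VR session and 0 for a tablet session. If every row has VR = 1, the data inform only the sum a + b, and the contrast b cannot be estimated. Unscheduled VR sessions add more rows with VR = 1 and change nothing. A mixed model can accommodate scattered gaps, but it cannot supply a condition that was never observed. This step shows what the literal reading implies. It is not evidence that data will in fact be lost.

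**Step 3. Can another planned measure stand in?** Heart rate is recorded before and after every session, but the text gives no method or recording length. Because the next sentence separately names continuous heart rate, the natural inference is that the before-and-after values are single readings, which would not give variability. The documents do not state this, nor do they say which recording heart rate variability is derived from.

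**Step 4. Assigning opioid use to a condition.** One VR and one tablet session fall on the same day. The readable text gives neither the interval between them nor a collection window. A dose given after both sessions has followed both conditions, so even a complete dose record needs a rule to assign it.

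**Step 5. Extra work if tablet sessions are added.** Two more collections of each measure per completer: 2 × 32 = 64 for the 32 patients in the sample size calculation, and at most 2 × 60 = 120 if all 60 enrolled patients complete.

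**The case against.** The strongest reply is that the protocol is silent about tablet sessions and does not exclude them. The collection sentence contains no word of restriction, and the sentence after it broadens the scope. The aims and the list of secondary outcomes presuppose control-side data, so a drafting omission is a likely explanation. A figure beside the session schedule is not shown, and the questionnaires that Procedures places later in the application are not visible. Either could hold the full schedule. All of this stands, so the point has to be about what the readable sentence plans and not about what the investigators intend.

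For opioid use there is a further argument. With no window stated, collection after a VR session could describe when usage is looked up and not the period it covers. A look-up after VR could then include time after a tablet session on the same day. This also stands: zero tablet collections is the literal reading and not an established fact. It does not rescue the contrast, however, because usage retrieved that way still could not be divided between the two conditions.

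Opioid doses might also be recoverable from medication records. The documents do not plan this, and they do not say whether continuous heart rate is stored.

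What the reply does not remove is the contrast within one paragraph between wording that covers every session and wording that names VR sessions, set against aims that need both conditions.

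**Conclusion.** The point holds in limited form. As written, Procedures plans opioid use and continuous heart rate after VR sessions and does not mention tablet sessions. If it is followed literally, Aim 1b and the heart rate variability part of Aim 1c have no planned control observations: 2 VR and 0 tablet collections per completer for each measure. The heart rate part rests on the inference that variability is derived from the continuous recording. The amount of data actually at risk cannot be computed from the documents.

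A reader might infer more, and the documents do not support it:

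- *That the protocol rules out tablet-side collection, or that the trial will have no control data.* The text is silent, and the figure or application material may fill the gap.
- *That Aim 1c as a whole fails.* Pupil measures are planned at every session.
- *That the primary outcome is compromised.* Pain is scored before and after every study session.

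This is a correction worth making because two secondary aims depend on it and it takes little text. It does not threaten the main comparison.

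**What to change.** In the Procedures sentence, add tablet sessions to VR sessions and state that opioid use and continuous heart rate are collected in the same way after both. If the figure or other application material already schedules this, bring the sentence into line with it.

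Because the two conditions share a day, add to Procedures or to Primary and Secondary Analyses that:

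- the collection window is the same for VR and tablet sessions, with its length chosen by the investigators;
- opioid doses are assigned to a session by their recorded time;
- the VR-versus-tablet contrast for these two measures rests on the scheduled, randomised sessions, since extra sessions are taken at the participant's wish.

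It would also help to state which recording heart rate variability is derived from.

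The text change is about one sentence in each section. The workload is two more collections of each measure per completer, 64 for 32 completers and at most 120 for 60. There is a trade-off in the window: a short one separates the sessions better but misses later opioid use. None of this removes carryover from the first session of a day to the second.

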### *Sample Size Calculation*

Because participants will serve as their own control, individual variability in experiencing and reporting pain will be reduced, enhancing our ability to identify treatment effects. A sample size of 32 patients will give us 80% power to observe a 30% difference in delta pain scores (our primary outcome). As many patients will be discharged prior to being able to complete the study. We will aim for an enrollment of 60 total patients.

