### *Research Related Risks*

1. Loss of Confidentiality: There is a minimal risk for a loss of confidentiality when participating in a research study. However, every step to ensure the confidentiality and anonymity of results and identity will be taken. Steps will include using only an assigned code number for personally identifiable information, including contact information and name, on any documentation from this study. Moreover, electronic data will be password-protected and all paper copies of data will be stored in a locked cabinet.

2. There is a minimal risk for a breach of privacy. However, to minimize this, consent will only be obtained in private patient rooms or in a private conference room.

3. There is a risk that patients may have a difficult time using the HMD and handheld controller, which may make them frustrated or upset. At this point, the research personnel will assist them in any way they can so that the patient can use the HMD and continue on with the study protocol. The research personnel is aware that the device can be difficult to use for first time users. The PI and research personnel have developed standards of procedures on how to address this issue if it were to arise.

4. Immersion in virtual reality may cause of a sense of being in a closed environment and rarely nausea. These effects are only transitory but if you experience any discomfort, the virtual

reality headset can be removed quickly. Patients who cannot tolerate the virtual reality will prematurely end study participation.

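### The closing VR-experience questionnaire has no planned administration for patients who leave early, so its results will come mainly from those who tolerated VR and finished

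*Combined protocol and SAP*

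**What the plan says.** The Procedures section plans questionnaires on three kinds of occasion: at baseline, around every session, and at the end. On the second, it says: "Before and after each session, participants will answer simple questions via questionnaire (included later in this application"). The items of that questionnaire are not in the supplied text. On the third: "At the conclusion of all sessions, participants will complete another questionnaire to help us understand their self-perceived experience of using virtual reality". This closing form is the only one described as covering the experience of VR, and no other time is given for it.

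Three groups may not reach that point:

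- **VR intolerance** (Research Related Risks, item 4): "Patients who cannot tolerate the virtual reality will prematurely end study participation".
- **Severe symptoms** such as dizziness or seizure (Research Related Risks, item 5): "the virtual reality headset will be removed and the study will be discontinued in the patient".
- **Early discharge** (Sample Size Calculation): "As many patients will be discharged prior to being able to complete the study". No rate is given.

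The Aims section lists "subjective experience measures (perceived effectiveness, anxiety") under Aim 1c, as a comparison of VR with non-immersive control sessions. Primary and Secondary Analyses makes these secondary outcomes. Neither section says which questionnaire supplies them.

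**The concern.** Leaving because VR is intolerable is caused by the very thing the closing form measures. If the form is given only when the programme is complete, the patients with the worst experience are the ones most likely to be missing from it. The loss is therefore informative and would favour VR.

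The planned analysis does not clearly repair this. Primary and Secondary Analyses relies on mixed effect models to use patients with incomplete data. That works for pain, which is rated around every session, so a patient who leaves after one session still contributes. A form given once, at the end, leaves no earlier value of itself for the model to use.

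Two readings are at stake. One is the description of how patients experienced VR. The other is the feasibility half of Aim 1a, where the accounts of patients who could not continue are among the most useful evidence.

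**Working it through.** **1. Timing set against exit routes.** Procedures specifies two VR and two tablet sessions, with two sessions per day: 4 / 2 = 2 days. Eligibility Criteria asks only for an expected stay of at least twelve hours after enrolment. The plan therefore admits patients who may go home before the programme ends. Intolerance and severe symptoms add two further exits. For none of the three does the text mention the closing form, or a rule for reporting patients who lack it.

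**2. The plan's own figure.** Sample Size Calculation states: "A sample size of 32 patients will give us 80% power to observe a 30% difference in delta pain scores (our primary outcome"). This cannot be rebuilt, because the standard deviation, the reference change, alpha and sidedness are not given. Assuming a two-sided alpha of 0.05, the implied standardised paired effect is (1.960 + 0.842) / √32 = 0.495 by the normal approximation. Nothing in the present point changes that calculation. It matters here only through the enrolment target: "We will aim for an enrollment of 60 total patients".

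**3. Enrolment margin.** 60 − 32 = 28, and 28 / 60 = 46.7%. Equivalently, 32 / (1 − 28/60) = 60. This is the largest share of non-completers that still leaves 32. It is not a forecast.

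**4. Illustration of the tilt from intolerance (assumed inputs).** Let *p* be the share who stop for intolerance. Assume that all of them would rate VR unfavourably, and that 80% of everyone else, including those discharged early, would rate it favourably. The finishers' figure is then 80%, and the figure for all exposed patients is (1 − *p*) × 0.80:

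| Assumed *p* | Finishers | All exposed |
|---|---|---|
| 5% | 80% | 0.95 × 0.80 = 76% |
| 10% | 80% | 0.90 × 0.80 = 72% |
| 15% | 80% | 0.85 × 0.80 = 68% |

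**5. Bounds with no assumption about those who leave.** Let *f* be the share finishing, and suppose that 80% of finishers are favourable. The all-enrolled share then lies between 0.80*f* and 0.80*f* + (1 − *f*):

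| Finishing, of 60 | *f* | Lower | Upper |
|---|---|---|---|
| 32 | 0.533 | 43% | 89% |
| 45 | 0.750 | 60% | 85% |
| 54 | 0.900 | 72% | 82% |

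The bounds show how little a finishers-only form would settle about everyone enrolled. They are not estimates of bias.

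**The case against.** A reader might infer that the whole Aim 1c subjective-experience result describes only patients who finished. The documents do not support that. Aim 1c compares VR with control sessions, and a single closing form about VR is a doubtful source for such a comparison. The questionnaires around each session, which early leavers give for every session they do, may supply perceived effectiveness and anxiety. Since their items are not in the supplied text, the effect on Aim 1c can only be conditional.

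A reader might also take 47% as the expected dropout. It is an enrolment margin. The plan attributes the anticipated losses to discharge, and nothing suggests that discharged patients would rate VR worse. In the illustration they rate it as finishers do, so the 47% adds nothing to the gap of 80% against 72%.

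The intolerance rates are likewise assumed. Known VR intolerance is an exclusion, and item 4 of Research Related Risks calls nausea rare and the effects transitory. Item 5 quotes a general-use figure of about 1 in 4000 for severe symptoms. If it transferred to these patients, 60 / 4000 = 0.015 events would be expected.

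The closing form's timing could also mean the end of whatever sessions a given patient does, since the number varies with optional extras. That reading is possible, but it fits poorly with text that ends participation prematurely, and staff could apply so open a trigger differently.

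Nor is intolerance itself hidden: staff stay with the patient during VR use, a stop is observable, and adverse events are reviewed weekly. What would be missing is the patient's own account.

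These arguments limit the scope and the size. They do not remove the gap: no exit administration is planned for the one form described as covering VR experience.

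**Conclusion.** The point holds for the closing questionnaire. Followed as written, its timing selectively loses the accounts of patients who stop because of VR, and the mixed model has no earlier value of that form to use. The likely direction is in favour of VR.

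The size cannot be derived from the documents. The 4 to 12 percentage points in the illustration (80% against 76% to 68%) rest on an assumed 5% to 15% intolerance, all unfavourable, and on an assumed 80% favourable rating among everyone else. At a lower intolerance rate the gap shrinks in proportion.

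The primary pain outcome, the sample size and the mixed model for repeated ratings are not affected. This is a worthwhile, inexpensive improvement to a secondary and feasibility measure, not a threat to the trial's main comparison.

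**What to change.** - **Timing.** In Procedures, offer the existing closing form, where the patient is able and willing, at the earliest of: the last scheduled session, a stop for intolerance or symptoms, withdrawal, or discharge.
- **Discontinuation text.** Align items 4 and 5 of Research Related Risks so that ending sessions does not rule out this one form. The rules for ending VR sessions are not in question.
- **Who is included.** Cover everyone exposed to the headset, including patients who stop during the tutorial.
- **Recording and reporting.** Record the exit reason and the number of VR and tablet sessions done. Report results for all exposed patients and by exit reason, with the number lacking the form.
- **Source of Aim 1c.** State which questionnaire supplies perceived effectiveness and which supplies anxiety.

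The cost is a wording change in two sections, a line in the analysis section, and one existing form at exit. Research staff are already present during VR use, so no new instrument or staff is needed. The downside is that some answers will rest on one VR session or less, which the recorded session counts would make visible.
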